7.4 Statistical Analyses for Safety

Safety analyses will be carried out using the Safety Analysis Set, which includes all subjects who receive at least 1 dose of study drug. Subjects will be grouped to the treatment actually received. Safety will be assessed by AEs, physical examination, laboratory assessments, ECGs, and vital signs. Frequency tables and lists of subjects with treatment-emergent adverse events (TEAEs) by preferred term as in the Medical Dictionary for Regulatory Activities (MedDRA®) dictionary, by system organ class, by severity, and by relationship to the study drug as assessed by the Investigator will be provided. The changes from Baseline in vital signs, physical examination results, and clinical laboratory values will be analyzed in a descriptive manner. Shift of laboratory values from Baseline to defined time points will be tabulated. Pre-treatment AEs will be summarized separately.

All TEAEs, SAEs, AEs leading to discontinuation, and AESI will be collected during the study. A TEAE is defined as an event with onset or worsening after the first study dose of study drug and within 30 days after the last dose of study drug administration. The number and percentages of subjects experiencing TEAEs will be tabulated using the MedDRA system organ class and preferred term. Summaries (including percentages and event per 100 patient-year) of SAEs, deaths, AEs leading to discontinuation, and AESI will be provided as well. For selected laboratory and vital signs parameters, mean change from Baseline and percentage of subjects with evaluations meeting pre-defined criteria for Potentially Clinically Important values will be summarized.

7.5 Interim Analysis

A planned unblinded interim analysis was performed when 50% of the planned subjects completed their Week 24 assessments. The objective of this analysis was to reassess the treatment regimens in Study M19-130 and the benefit/risk for rollover into LTE Study M20-186.

The interim analysis was performed by an independent team at AbbVie that is separate and apart from the blinded study team. The M19-130 study team will remain blinded through the Week 24 Primary Analysis.

An Interim Unblinding Plan (IUP) was developed separately describing the analyses to be performed and included execution logistics, an unblinded analysis team, and the data chain of custody to protect the integrity of the study.

An Internal Executive Review Committee (IERC) reviewed the interim unblinded results as specified in the IERC charter and decided which treatment group(s) should be continued in Study M19-130 and for rollover into LTE Study M20-186.

Study sites and subjects remained blinded to treatment assignment in Study M19-130 and LTE Study M20-186 throughout the studies.

7.6 Overall Type I Error Control

All tests will be performed as pairwise comparison at a 2-sided statistical significance level of $\alpha = 0.1$. No multiplicity adjustment will be applied because this is a Phase 2 study.

7.7 Sample Size Estimation

The planned sample size for this study is 325 subjects in total, with 65 subjects for each of the 5 groups, determined based on the primary endpoint, the composite of SRI-4 and steroid dose ≤ 10 mg prednisone equivalent QD at Week 24. Assuming at Week 24 the placebo response rate is 25%, a two-sided χ^2 test with $\alpha = 10\%$ will provide 78% to 91% power to detect a difference of 20% to 25% between an active treatment group and the placebo group.

8 ETHICS

8.1 Independent Ethics Committee/Institutional Review Board (IEC/IRB)

The protocol, informed consent form(s), recruitment materials, and all subject materials will be submitted to the IEC/IRB for review and approval. Approval of both the protocol and the informed consent form(s) must be obtained before any subject is enrolled. Any amendment to the protocol will require review and approval by the IEC/IRB before the changes are implemented to the study. In addition, all changes to the consent form(s) will be IEC/IRB approved.

In Japan, the investigator will prepare the consent form and explanatory material required to obtain subject's consent to participate in the study with the cooperation of the sponsor and will revise these documents as required. The prepared or revised consent forms and explanatory material will be submitted to the sponsor. Approval of the IRB will be obtained prior to use in the study.

In Japan, when important new information related to the subject's consent becomes available, the investigator will revise the consent form and explanatory material based on the information without delay and will obtain the approval of the IRB prior to use in the study. The investigator will provide the information, without delay, to each subject already participating in the study, and will confirm the intention of each subject to continue the study or not. The investigator shall also provide a further explanation using the revised form and explanatory material and shall obtain written consent from each subject of their own free will to continue participating in the study.

8.2 Ethical Conduct of the Study

The study will be conducted in accordance with the protocol, Operations Manual, International Council for Harmonisation (ICH) guidelines, applicable regulations, and guidelines governing clinical study conduct and the ethical principles that have their origin in the Declaration of Helsinki. Responsibilities of the investigator are specified in [Appendix B](#).

8.3 Subject Confidentiality

To protect subjects' confidentiality, all subjects and their associated samples will be assigned numerical study identifiers or "codes." No identifiable information will be provided to AbbVie.

9 SOURCE DOCUMENTS AND CASE REPORT FORM COMPLETION

The investigator is responsible for ensuring the accuracy, completeness, legibility, and timeliness of the data reported. All source documents should be attributable, legible, contemporaneous, original, accurate, and complete to ensure accurate interpretation of data. Clinical site monitoring is conducted to ensure that the rights and well-being of human subjects are protected, that the reported trial data

are accurate, complete, and verifiable, and that the conduct of the trial is in compliance with the currently approved protocol, ICH Good Clinical Practice (GCP), and applicable local regulatory requirement(s). During the COVID-19 pandemic, remote data review and verification of data may be employed if allowed by the local regulatory authority, IRB/IEC, and the study site.

10 DATA QUALITY ASSURANCE

AbbVie will ensure that the clinical trial is conducted with a quality management system that will define quality tolerance limits in order to ensure human subject protection and reliability of study results. Data will be generated, documented, and reported in compliance with the protocol, ICH GCP, and applicable regulatory requirements.

11 COMPLETION OF THE STUDY

The Investigator will conduct the study in compliance with the protocol and complete the study within the timeframe specified in the contract between the Investigator (and Director of the site in Japan) and AbbVie. Continuation of this study beyond this date must be mutually agreed upon in writing by both the Investigator (and Director of the site in Japan) and AbbVie. The investigator will provide a final report to the IEC/IRB following conclusion of the study and will forward a copy of this report to AbbVie or their representative.

The Investigator (and Director of the site in Japan) must retain any records related to the study according to local requirements. If the Investigator is not able to retain the records, he/she must notify AbbVie to arrange alternative archiving options.

AbbVie will select the signatory Investigator from the Investigators who participate in the study. Selection criteria for this Investigator will include level of participation as well as significant knowledge of the clinical research, investigational drug, and study protocol.

This study will be conducted in compliance with the protocol, GCP, and all other applicable regulatory requirements, including the archiving of essential documents.

The end-of-study is defined as the date of the last subject's last visit, or date of the last follow-up contact, whichever is later.

APPENDIX A. STUDY SPECIFIC ABBREVIATIONS AND TERMS

Abbreviation	Definition
Ab	Antibody
ACR	American College of Rheumatology
ADL	Activities of daily living
AE	Adverse event
AESI	Adverse events of special interest
Ag	Antigen
ALT	Alanine transaminase
ANA	Antinuclear antibody
ANC	Absolute neutrophil count
anti-dsDNA	Anti-double stranded DNA
AO	As observed
AST	Aspartate transaminase
axSpA	Axial spondyloarthritis
BCG	Bacilli Calmette-Guérin
BICLA	BILAG-Based Combined Lupus Assessment
BILAG	British Isles Lupus Assessment Group
BL	Baseline
BP	Blood pressure
BTK	Bruton's tyrosine kinase
CAC	Cardiovascular Adjudication Committee
Cardiac	Cardiovascular
CD	Crohn's disease
CIS	Carcinoma in-situ
CL/F	Apparent clearance
CLASI	Cutaneous Lupus Erythematosus Disease Area and Severity Index
CMH	Cochran-Mantel-Haenszel
CNS	Central nervous system
COVID-19	Coronavirus disease 2019
CPK	Creatine Phosphokinase
CRF	Case report form
CT	Computed tomography

CTCAE	Common Terminology Criteria for Adverse Events
CVA	Cerebrovascular accident
CXR	Chest x-ray
CYP3A	Cytochrome P450 3A isoform subfamily
CYP1A2	Cytochrome P450 1A2 isoform subfamily
DMC	Data Monitoring Committee
DNA	Deoxyribonucleic acid
dsDNA	Double stranded deoxyribonucleic acid
ECG	Electrocardiogram
eCRF	Electronic case report form
EU	European Union
EudraCT	European Clinical Trials Database
FACIT	Functional Assessment of Chronic Illness Therapy
FAS	Full analysis set
FSH	Follicle-stimulating hormone
GCA	Giant cell arteritis
GCP	Good clinical practice
GCSF	Granulocyte-colony stimulating factor
GFR	Glomerular filtration rate
GI	Gastrointestinal
GM-CSF	Granulocyte-macrophage colony-stimulating factor
HB	Hepatitis B
HBc Ab	Hepatitis B core antibody
HBs Ag	Hepatitis B surface antigen
HBV	Hepatitis B virus
HCV	Hepatitis C virus
HCV Ab	Hepatitis C virus antibody
HIV	Human immunodeficiency virus
HIV Ab	HIV antibody
IC ₅₀	Inhibitory concentration producing 50% inhibition
ICH	International Council for Harmonisation
IEC	Independent ethics committee
IEC/IRB	Independent Ethics Committee/Institutional Review Board
IERC	Internal Executive Review Committee

IFN	Interferon
IgG	Immunoglobulin G
IgM	Immunoglobulin M
IM	Intramuscular
IMP	Investigational Medicinal Product
IRB	Institutional review board
IRT	Interactive response technology
IU	International Unit
IUD	Intrauterine device
IUS	Intrauterine hormone-releasing system
IV	Intravenous
IVIG	Intravenous immunoglobulin
JAK	Janus kinase
JAK1	Janus kinase 1
JAK2	Janus kinase 2
JAK3	Janus kinase 3
JIA	Juvenile idiopathic arthritis
LLDAS	Lupus Low Disease Activity State
LTE	Long-term extension
LupusQoL	Lupus Quality of Life questionnaire
MACE	Major adverse cardiovascular event
MDRD	Modification of Diet in Renal Disease
MedDRA	Medical Dictionary for Regulatory Activities
MI	Myocardial infarction
MMRM	Mixed-effect Model Repeated Measures
MTX	Methotrexate
N/A	Not applicable
NCI	National Cancer Institute
NMSC	Non-melanoma skin cancer
NRI-C	Non-Responder Imputation while incorporating Multiple Imputation to handle missing data due to CCOVID-19
NRS	Numerical rating scale
NSAID	Nonsteroidal anti-inflammatory drug
OC	Observed Case

PBMC	Peripheral blood mononuclear cell
PCR	Polymerase chain reaction
PD	Premature Discontinuation
PhGA	Physician's Global Assessment
PI	Principal Investigator
PK	Pharmacokinetic(s)
PPD	Purified protein derivative (tuberculin)
PRN	As needed
PRO	Patient-reported outcome
PtGA	Patient global assessment
QD	Once a day
QTc	QT interval corrected for heart rate
QTcF	QT interval corrected for heart rate using Fridericia's formula
RA	Rheumatoid arthritis
RCT	Randomized clinical trial
REML	Restricted maximum likelihood
RNA	Ribonucleic acid
ROA	Route of administration
SAE	Serious adverse event
SAP	Statistical analysis plan
SAR	Serious adverse reaction
SELENA	Safety of Estrogens in Lupus Erythematosus National Assessment
SF-36	36-Item Short Form Health Survey
SFI	SLEDAI Flare Index
SLE	Systemic lupus erythematosus
SLEDAI	Systemic Lupus Erythematosus Disease Activity Index
SLEDAI-2K	Systemic Lupus Erythematosus Disease Activity Index 2000
SJC	Swollen joint count
SLICC	Systemic Lupus Erythematosus International Collaborating Clinics
SRI	SLE Responder Index
SUSAR	Suspected unexpected serious adverse reaction
TA MD	Therapeutic Area MD
TB	Tuberculosis
TBNK	T lymphocytes, B lymphocytes, and natural killer lymphocytes

TEAE	Treatment-emergent adverse event
TJC	Tender joint count
TNF	Tumor necrosis factor
UC	Ulcerative colitis
UK	United Kingdom
ULN	Upper limit of normal
UPCR	Urine protein to creatinine ratio
US	United States
vs	versus
V_{ss}/F	Apparent volume of distribution at steady state
WBC	White blood cells
WOCBP	Women of Childbearing Potential

APPENDIX D. ACTIVITY SCHEDULE

The following table shows the required activities across all subject encounters. The individual activities are described in detail in the **Operations Manual**. Allowed modifications due to COVID-19 are detailed within the **Operations Manual**.

Study Activities Table

	Screening	Baseline	Week 2	Week 4	Week 8	Week 12	Week 16	Week 20	Week 24	Week 28	Week 32	Week 36	Week 40	Week 44	Week 48/ Premature Discontinuation	30-Day Follow Up Phone Call*
Visit Window (Days)			± 3	± 7												
INTERVIEWS & QUESTIONNAIRES																
Subject information and informed consent	✓															
Eligibility criteria	✓	✓														
Medical/surgical history ^a	✓	✓														
Adverse event (AE) and AE of special interest (AESI) assessment	✓	✓	✓	✓	✓	✓	✓	✓	✓	✓	✓	✓	✓	✓	✓	✓
Prior/concomitant therapy ^a	✓	✓	✓	✓	✓	✓	✓	✓	✓	✓	✓	✓	✓	✓	✓	✓
Steroid therapy assessment	✓	✓	✓	✓	✓	✓	✓	✓	✓	✓	✓	✓	✓	✓	✓	✓
Patient-Reported Outcome ^b • PtGA		✓	✓	✓	✓	✓	✓	✓	✓	✓	✓	✓	✓	✓	✓	
Patient-Reported Outcomes ^b • LupusQoL • FACIT-Fatigue • SF-36 • Pain NRS		✓	✓			✓			✓						✓	
Verification of continued contraceptive measures for WOCBP		✓	✓	✓	✓	✓	✓	✓	✓	✓	✓	✓	✓	✓	✓	
Physician Global Assessment (PhGA) ^c	✓	✓	✓	✓	✓	✓	✓	✓	✓	✓	✓	✓	✓	✓	✓	
TB risk assessment form	✓															
SLEDAI-2K and BILAG assessments	✓	✓		✓	✓	✓	✓	✓	✓	✓	✓	✓	✓	✓	✓	
CLASI assessment	✓	✓		✓	✓	✓	✓	✓	✓	✓	✓	✓	✓	✓	✓	

	Screening	Baseline	Week 2	Week 4	Week 8	Week 12	Week 16	Week 20	Week 24	Week 28	Week 32	Week 36	Week 40	Week 44	Week 48/ Premature Discontinuation	30-Day Follow Up Phone Call*
Visit Window (Days)			± 3	± 7												
SELENA SLEDAI Flare Index assessment				✓	✓	✓	✓	✓	✓	✓	✓	✓	✓	✓	✓	
Verification of continued benefit of subject participation									✓							
LOCAL LABS & EXAMS																
Chest x-ray	✓															
12-lead ECG	✓		✓	✓	✓	✓	✓	✓	✓			✓			✓	
Height (screening only) and weight	✓	✓	✓	✓	✓	✓	✓	✓	✓	✓	✓	✓	✓	✓	✓	
Vital signs	✓	✓	✓	✓	✓	✓	✓	✓	✓	✓	✓	✓	✓	✓	✓	
Physical examination ^d	✓	✓	✓	✓	✓	✓	✓	✓	✓	✓	✓	✓	✓	✓	✓	
TJC28/SJC28	✓	✓		✓	✓	✓	✓	✓	✓	✓	✓	✓	✓	✓	✓	
Urine pregnancy test (for WOCBP only) ^e		✓	✓	✓	✓	✓	✓	✓	✓	✓	✓	✓	✓	✓	✓	
Skin Photographs ^f	✓								✓							
CENTRAL LABS																
HIV Testing (if not prohibited by local regulation)	✓															
HBs Ag, HBc Ab, HCV Ab ^g	✓															
Complement C3, C4 testing	✓	✓	✓	✓	✓	✓	✓	✓	✓	✓	✓	✓	✓	✓	✓	
anti-dsDNA	✓	✓	✓	✓	✓	✓	✓	✓	✓	✓	✓	✓	✓	✓	✓	
ANA/anti-Smith	✓															
Cotinine lab measurement	✓															
Prothrombin, Partial Thromboplastin		✓														
Lupus Anticoagulant, Anti-Beta 2 Glycoprotein 1, Anticardiolipin Antibody	✓															

	Screening	Baseline	Week 2	Week 4	Week 8	Week 12	Week 16	Week 20	Week 24	Week 28	Week 32	Week 36	Week 40	Week 44	Week 48/ Premature Discontinuation	30-Day Follow Up Phone Call*
Visit Window (Days)			± 3	± 7												
Serum pregnancy test (WOCBP), FSH (non-WOCBP presumed post-menopausal)	✓															
QuantiFERON-TB Gold test (and/or local PPD skin test, T-SPOT.TB Test)	✓															
Clinical chemistry, Hematology (CBC), Urinalysis, Urine Protein to Creatinine ratio (UPCR)	✓	✓	✓	✓	✓	✓	✓	✓	✓	✓	✓	✓	✓	✓	✓	
IgG and IgM	✓	✓		✓					✓						✓	
Blood samples for elsubrutinib and upadacitinib pharmacokinetic (PK) analysis		✓ ^h		✓ ^{h,i}		✓ ^{i,j}		✓ ^{h,i}	✓ ^{h,i}						✓ ^{i,k,l}	
Biomarkers Sample: Whole blood for BTK occupancy analysis (only select # of sites and subjects in the US) ^m		✓ ⁿ				✓ ⁱ			✓ ^h						✓ ^{k,l}	
Biomarker Sample: Whole blood for BTK Y223 phosphorylation assay ^m		✓ ⁿ				✓ ⁱ			✓ ^h						✓ ^{k,l}	
Biomarker Sample: Whole Blood (plasma, serum, DNA and RNA) ^{m,o}		✓ ^j	✓ ^l	✓ ^l		✓ ^l			✓ ^l						✓ ^l	
Biomarker Sample: Whole Blood viable PBMCs ^m		✓ ^j	✓ ^l	✓ ^l		✓ ^l			✓ ^l						✓ ^l	
Biomarker Sample: Whole Blood: Immunophenotyping (TBNK, B cell subsets) ^m		✓ ^j		✓ ^l		✓ ^l			✓ ^l						✓ ^{k,l}	
Biomarker Sample: Interferon signature ^m	✓			✓					✓						✓ ^k	
Rx TREATMENT																
Randomization/drug assignment		✓														
Dispense study drug ⁱ		✓		✓	✓	✓	✓	✓	✓	✓	✓	✓	✓	✓		

	Screening	Baseline	Week 2	Week 4	Week 8	Week 12	Week 16	Week 20	Week 24	Week 28	Week 32	Week 36	Week 40	Week 44	Week 48/ Premature Discontinuation	30-Day Follow Up Phone Call*
Visit Window (Days)			± 3	± 7												
Dispense subject diaries		✓														
Review and copy subject dosing diary and perform drug reconciliation ⁱ			✓	✓	✓	✓	✓	✓	✓	✓	✓	✓	✓	✓	✓	

ANA = antinuclear antibody; anti-dsDNA = anti-double stranded DNA; BILAG = British Isles Lupus Assessment Group; BTK = Bruton's tyrosine kinase; CBC = complete blood count; CLASI = Cutaneous Lupus Erythematosus Disease Area and Severity Index; DNA = deoxyribonucleic acid; ECG = electrocardiogram; FACIT = Functional Assessment of Chronic Illness Therapy; FSH = follicle stimulating hormone; HBc Ab = hepatitis B core antibody; HBs Ag = hepatitis B surface antigen; HCV Ab = hepatitis C virus antibody; HIV = human immunodeficiency virus; IgG = immunoglobulin G; IgM = immunoglobulin M; LupusQoL = Lupus Quality of Life questionnaire; Pain NRS = pain numerical rating scale; PBMC = peripheral blood mononuclear cell; PPD = purified protein derivative (tuberculin); PtGA = patient global assessment; RNA = ribonucleic acid; SF-36 = 36-Item Short Form Health Survey; SELENA = Safety of Estrogens in Lupus Erythematosus National Assessment; SJC = swollen joint count; SLEDAI = Systemic Lupus Erythematosus Disease Activity Index; TB = tuberculosis; TBNK = T lymphocytes, B lymphocytes, and natural killer lymphocytes; TJC = tender joint count; US = United States; WOCBP = women of childbearing potential

- * The 30-day follow up call will be calculated from the last study drug administration date/last visit for all subjects not entering the long-term extension LTE Study M20-186.
- a. A complete medical history and prior/concomitant therapy will be taken at Screening and will be updated at the Baseline Visit.
- b. The patient-reported outcome instrument should be completed prior to drug administration on Day 1 and prior to any discussion of adverse events or any review of laboratory findings. The subject should complete the questionnaires before site personnel perform any clinical assessments and before any interaction with site personnel has occurred to avoid biasing the subject's response.
- c. This is a clinician-reported outcome that is completed on the tablet.
- d. A complete physical examination will be performed during Screening and Study Day 1. Physical examinations at other visits can be symptom-directed.
- e. Urine pregnancy test will be performed locally as indicated in the table for all females of childbearing potential. The urine pregnancy test must be negative to receive study drug. If any urine pregnancy test is positive, a serum pregnancy test will be performed by the central laboratory.
- f. Any subject who has a positive skin score at screening (i.e., Principal Investigator [PI] believes they have a Lupus rash) needs photos for adjudication; photos will only be collected for subjects presenting with a possible Lupus rash during Screening and at Week 24 for those who have a confirmed (by adjudicator) Lupus rash at screening.
- g. Subjects will be tested for the presence of the hepatitis B and C virus (HBV and HCV) at Screening. A positive result for the hepatitis B surface antigen (HBs Ag) or hepatitis C (HCV RNA detectable for any subject with positive anti-HCV Ab) will be exclusionary. For subjects who are negative for HBsAg but positive for core antibody (HBc Ab), HBV DNA polymerase chain reaction (PCR) will be performed and any result that meets or exceeds detection sensitivity will be exclusionary.
- h. Post-dose collection.
- i. Not required if subject discontinues study drug but remains in the study.
- j. Pre-dose collection.
- k. To be completed at Premature Discontinuation only.
- l. Collection at any time during visit.
- m. Will not be collected in China.

- n. Pre-dose and post-dose collection.
- o. Blood samples collected and analyzed from all subjects unless precluded by local regulations or restrictions.

APPENDIX E. DESCRIPTION OF EFFICACY MEASURES

Measure	Definition	Scale
Systemic Lupus Erythematosus Responder Index (SRI) ¹³	Composite responder index based on improvement in disease activity (number following SRI indicates numerical improvement in SLEDAI-2K score) without worsening of the overall condition (no worsening in PhGA, < 0.3 point increase) or the development of significant disease activity in new organ systems (no new BILAG A or > 1 new BILAG B).	Not Applicable
British Isles Lupus Assessment Group Based Combined Lupus Assessment (BICLA) ¹⁴	Composite responder index based on improvement in organ systems (improvement in all initial A and B scores, no more than one new BILAG B score) without worsening of the overall condition (no worsening in PhGA, < 0.3 point increase) and no worsening of SLEDAI-2K score.	Not Applicable
Lupus Low Disease Activity State (LLDAS) ¹⁵	A state of low disease activity based on SLEDAI score (SLEDAI-2K score ≤ 4 excluding SLEDAI-2K activity in major organ systems), absence of SLE disease activity in major organ systems and new disease activity, Physician's Global Assessment (PhGA ≤ 1), and concomitant medication usage (steroid dose ≤ 7.5 mg QD and toleration of immunosuppressive drugs at standard maintenance doses).	Not Applicable
Systemic Lupus Erythematosus Disease Activity Index 2000 (SLEDAI-2K) ¹⁶	Global SLE disease activity index that focuses on high-impact disease manifestations across 9 organ systems. It includes 24 clinical and laboratory variables with manifestations weighted by the affected organ system.	Scores range from 0 to 105, with higher scores indicating more severe disease
British Isles Lupus Assessment Group (BILAG) 2004 ¹⁷	Global SLE disease activity index designed on the basis of the physician's intention to treat, focusing on changes in disease manifestations. The instrument assesses 97 clinical signs, symptoms, and laboratory parameters across 9 organ systems.	Letter score assigned to each organ system with following indications: A = severe, B = moderate, C = mild, D = inactive with prior history, and E = inactive with no history

Measure	Definition	Scale
Cutaneous Lupus Erythematosus Disease Area and Severity Index (CLASI) ¹⁸	Index used to assess cutaneous manifestations of SLE summarizing the activity of the disease.	Scores range from 0 to 70, with higher scores indicating more severity
SELENA SLEDAI Flare Index (SFI) ¹⁹	An index defining SLE flares using changes in the SLEDAI score, definitions of worsening signs and symptoms, treatment changes, and Physician's Global Assessment of Disease Activity.	Mild/moderate or severe flare
Physician's Global Assessment of Disease Activity ¹⁹	Physician's assessment of patient's overall disease activity due to SLE, as compared with all possible patients with SLE. The benchmarks of the visual analog scale are 0, 1, 2, and 3 on the line corresponding to no, mild, moderate, and severe SLE disease activity, respectively.	Visual-analog scale ranging from 0 to 3, with higher values indicating more severe disease

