The British Isles Lupus Assessment Group (BILAG) 2004 evaluates specific manifestations over the previous four weeks in a total of 8 organs systems, 9 in the revised Index: constitutional, mucocutaneous, neuropsychiatric, musculoskeletal, cardiorespiratory, gastrointestinal (GI), ophthalmic, renal, and hematological. Activity in each organ system is scored as: A = severe disease; B = moderate activity; C = mild disease; D = previous involvement, currently inactive; E = no previous activity. The BILAG also is used to evaluate the occurrence of flares in patients with SLE. A severe flare is defined as a score of A, new appearance and a moderate flare is defined with a score of B, and a reoccurrence is defined with a score of D or E.

The BILAG-Based Combined Lupus Assessment (BICLA)

The BILAG-Based Combined Lupus Assessment (BICLA) is a composite index used in clinical trials. This differs from the SLE Responder Index (SRI) in that the BILAG-2004 index is the driver of efficacy. BICLA requires patients to meet response criteria across the BILAG-2004 index, SLEDAI-2K, and PhGA. To be classified as a BICLA responder, patients must meet the following criteria: BILAG-2004 index improvement in all A and B scores, no more than one new BILAG B score, no worsening of the total SLEDAI-2K score from Baseline, no significant deterioration (not > 10% worsening) in the 100 mm visual

analogue PhGA and no treatment failure. The BICLA also identifies deterioration in clinical features and excludes treatment failures.

Cutaneous Lupus Erythematosus Disease Area and Severity Index (CLASI) assessment

The CLASI is a simple, single-page tool that separately quantifies disease activity and damage. Each part of the body is listed separately, from the scalp to the feet, in addition to sections focusing on mucous membrane involvement and alopecia. Scores for each area are assigned based on the most severe lesion within the area of interest. Of note, affected body parts are weighted equally regardless of surface area and number of lesions present. The selection of these equally weighted segments was designed to reflect the impact of more common areas of SLE skin involvement. Unlike the SLEDAI and BILAG, interim disease between visits is not accounted for, only the condition on the day of the examination.

SELENA SLEDAI Flare Index assessment

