3.0 Endpoints

3.1 Primary Endpoint(s)

The following is the primary efficacy endpoint:

- Achievement of SRI-4 and steroid dose ≤ 10 mg prednisone equivalent once a day (QD) at Week 24

SLE Responder Index (SRI)-4 is defined as follows with all criteria compared to baseline:

- ≥ 4 -point reduction in Systemic Lupus Erythematosus Disease Activity Index 2000 (SLEDAI-2K) score.
- No worsening of the overall condition (< 0.3 point increase in Physician's Global Assessment [PhGA])
- No new BILAG A or more than 1 new BILAG B disease activity scores (i.e., no organ system changes from baseline B/C/D/E to A and no more than 1 organ system changes from baseline C/D/E to B).

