25. Achievement of Clinical SLEDAI (defined as ≥ 4 -point reduction in clinical components (no laboratory components) of the SLEDAI) Among subjects with baseline SLEDAI-2K clinical score ≥ 4 .
26. Achievement of prednisone equivalent steroid daily dose ≤ 7.5 mg among subjects with daily dose ≥ 10 mg at Baseline through Week 48.
27. Achievement of prednisone equivalent steroid daily dose ≤ 7.5 mg sustained from Week 36 to Week 48 among subjects with daily dose ≥ 10 mg at Baseline.
28. Achievement of no increase in SLEDAI-2K total score from baseline.
29. Achievement of < 0.3 point increase in PhGA from baseline.
30. Achievement of no new BILAG A or more than 1 new BILAG B comparing to baseline (as defined in SRI-4).
31. Achievement of improvement in all baseline BILAG A and BILAG B (as defined in BICLA)

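### Neither written BICLA definition excludes a new BILAG A in an organ system that was C, D or E at baseline, and the visible SAP text gives no definition of its own

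*Protocol*

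**What the plan says.** BICLA is spelled out in two places, both in the protocol document.

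- **Protocol Appendix E.** The BILAG part is "improvement in all initial A and B scores, no more than one new BILAG B score". The rest is "without worsening of the overall condition (no worsening in PhGA, < 0.3 point increase) and no worsening of SLEDAI-2K score".
- **Operations Manual Section 3.11.** The BILAG part is "BILAG-2004 index improvement in all A and B scores, no more than one new BILAG B score". The SLEDAI-2K total must not worsen, PhGA may not worsen by more than 10% on a 100 mm line, and the list ends "analogue PhGA and no treatment failure". A closing sentence adds: "The BICLA also identifies deterioration in clinical features and excludes treatment failures". Treatment failure is not defined there.

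For SRI, the same documents name a new A outright. The SRI row of Appendix E has "no new BILAG A or > 1 new BILAG B". SAP 3.1 has "No new BILAG A or more than 1 new BILAG B disease activity scores" and translates it into transitions: no organ system may go from B, C, D or E to A, and at most one may go from C, D or E to B.

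The SAP uses BICLA as secondary endpoint 2 (3.2), as an additional endpoint (3.3), in the descriptive summaries for terminated groups (8.1) and in the interim analysis (11.2.3). It does not define it. In SAP 3.3, endpoint 31 reads "Achievement of improvement in all baseline BILAG A and BILAG B (as defined in BICLA", while endpoint 30, the component that bars a new A, is attributed to SRI-4.

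**The concern.** On the trial's own BILAG scale, A is severe and B is moderate. A response rule that caps new moderate activity and is silent on new severe activity runs against the purpose of the endpoint. A programmer who follows Appendix E, the Operations Manual and the labels on SAP endpoints 30 and 31 has no written basis for adding a no-new-A condition to BICLA. A subject with new severe disease in a previously quiet organ system could then be counted as a responder on a secondary endpoint that SAP 8.1 tests against placebo at two-sided 0.1.

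Separately, the two texts do not state the same PhGA limit, and only one of them mentions treatment failure. The source for the final program is therefore not settled.

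**Working it through.** The plan gives no BICLA response rate, and no power figure rests on BICLA, so there is no stated number to reproduce. The check applies the written rules to transitions.

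**Step 1. The rules.** Order the scores A > B > C > D > E.

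- BICLA, BILAG part as written: every organ system at A or B at baseline ends lower, and at most one goes from C, D or E to B. Any step down is taken as improvement; this assumption does not affect the result for a new A.
- SRI-4, BILAG part (SAP 3.1): none goes from B, C, D or E to A, and at most one goes from C, D or E to B.

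**Step 2. Apply them.** Take a subject with one organ system going from B to C, so that the improvement condition is met there, and vary the others.

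| Change in the other organ system(s) | BICLA as written | SRI-4, BILAG part | BICLA plus no new A |
|---|---|---|---|
| A to A | fails | passes | fails |
| B to A | fails | fails | fails |
| C to A | **passes** | fails | fails |
| D to A | **passes** | fails | fails |
| E to A | **passes** | fails | fails |
| two, each C to B | fails | fails | fails |
| two, each C to A | **passes** | fails | fails |

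The gap is C, D or E to A only. Inside it, the written rule rejects two new moderate scores and accepts two new severe ones.

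**Step 3. Do the other conditions close the gap?** Not by rule.

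- The SLEDAI-2K condition concerns the total, so a rise from new disease can be offset by improvement elsewhere. The organ list for BILAG in Operations Manual 3.11 also includes gastrointestinal and ophthalmic disease, which the SLEDAI-2K list there does not name.
- PhGA is a single global rating.
- The absence of treatment failure is required in one text only, without a definition.

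**Step 4. The PhGA limits side by side.** The trial's PhGA runs from 0 to 3 (Appendix E) on a 3-inch line (Operations Manual 3.11), not on a 100 mm line. If the 10% refers to the length of the scale, it is 0.10 × 3 = 0.3. An increase of exactly 0.3 then satisfies the Operations Manual (not more than 10%) and fails Appendix E (less than 0.3).

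**Step 5. Size.** With 65 planned subjects per arm, one reclassified subject moves that arm's rate by 1/65 = 0.0154, or 1.5 percentage points. The documents give no frequency of new BILAG A scores, so nothing beyond this unit can be calculated.

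**The case against.** The strongest reply has three parts.

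**The remaining conditions leave few such subjects.** A subject with a new A must still improve in every baseline A and B organ system, have no rise in SLEDAI-2K and have almost no rise in PhGA. Severe new disease should often move PhGA. This stands as a limit on the size of the effect, but these are indirect filters and none of them names a new A.

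**The intercurrent-event rules may catch the rest.** SAP 8.2.2 covers rescue medication and starting or raising SLE-related corticosteroid. It applies to all categorical endpoints, and SAP 8.3 makes subjects non-responders from such an event on. Appendix E describes BILAG as built on the physician's intention to treat, so a new A may often lead to treatment. The detailed rules are redacted, so their reach cannot be judged. Even so, a rule triggered by treatment is not a BICLA criterion, and a new A that triggers no listed event would remain.

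**The programs may use one shared variable.** The only new-activity component among SAP endpoints 28 to 31, and the only BILAG variable in the random-seed table (SAP Appendix E), is the one that bars a new A. That may mean it serves BICLA too. But endpoint 30 ties it to SRI-4, and the seed table has no variable for BILAG improvement, so the inference is weak. It is also possible that the cap on new B scores was meant to cover B or worse; the text does not say so, and the adjacent SRI row names A separately.

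A reader might also infer that the omitted treatment-failure condition in Appendix E by itself produces two response rates. That is not shown: if the 8.2.2 rules supply the condition at analysis, both texts may agree on it. The difference that can be shown on the page is the PhGA limit.

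**Conclusion.** The gap is real and is wrong as written: both definitions, taken literally, let a new A from C, D or E meet the BILAG part of BICLA, and they are stricter on moderate than on severe new disease. It should be corrected. It is a gap in wording; nothing shows a deliberate choice to tolerate a new A.

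The conclusion rests on the literal text and on the visible part of the SAP. Four stronger readings are not supported:

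- That any new A can pass. A move from B to A already fails.
- That the BICLA rate is overstated by some number of points, or more in one arm than another. The documents give no rate of new A scores; only the 1.5 points per subject follows from them.
- That the primary result is affected. Its SRI-4 component excludes a new A.
- That the correction bears on the interim decision. Protocol 7.5 reports that analysis as done, and terminated groups receive descriptive summaries only.

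**What to change.** State one BICLA definition in SAP 3.2, have every other use of BICLA refer to it, and align Protocol Appendix E and Operations Manual 3.11 with it:

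- improvement in every baseline BILAG A and B score;
- no new BILAG A and no more than one new BILAG B, in the transition terms of SAP 3.1;
- no increase in SLEDAI-2K total score from baseline;
- PhGA increase below 0.3 on the trial's 0 to 3 scale, replacing the 10% limit on a 100 mm line;
- no treatment failure, with the sponsor confirming whether the events in SAP 8.2.2 are what that term means. The visible text does not link the two.

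The cost is a short SAP entry and two matching edits. The BICLA response rate may fall slightly. If the programs already exclude a new A, only the text changes. Sample size, power, the primary endpoint and the completed interim analysis are unaffected.
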